1. INTRODUCTION

This Statistical Analysis Plan (SAP) describes the planned statistical data analyses of the long-term single-arm open-label study AC-065A303/GRIPHON OL (A303) for the purpose of the Clinical Study Report (CSR).

All enrolled participants were rolled over from the preceding double-blind study AC-065A302/GRIPHON (A302) without any wash-out period. With respect to safety assessment for long-term use of selexipag, safety data for the selexipag treatment in A302 study (median exposure duration 18.8 months) cannot be disregarded. Therefore, the interim A303 data (cut-off date on the 01 September 2019) and A302 data were concatenated for the supplemental New Drug Application (sNDA) / Marketing Authorization Application (MAA) submissions for the long-term selexipag safety and survival in PAH as well as for update of the Risk Management Plan (RMP).

For the A303 CSR, the following two types of safety information will be provided:

- Safety information collected under the A303 study.
- Safety information collected during selexipag treatment under the A302 and/or A303 studies (Completed summary at the end of A303 study can be used to update the sNDA/MAA tables – selexipag treated set based on 01 September 2019 cut-off).

This SAP refers to the documents listed in [Table 1](#).

Table 1: Key Reference Documents

| Document | Date, Version |
|---|---|
| Study Protocol AC-065A303 (GRIPHON OL) | Final version 9 (D-19.045 / EDMS-RIM-264143) |
| CRF specifications (GRIPHON OL) | Final Version: 20 May 2010 |
| CRF specifications (GRIPHON) | Final Version: 12 May 2010 |
| SAP for labeling update – long term survival | Final version 2 (D-19.320 / EDMS-RIM-265325) |
| Summary of Clinical Safety – selexipag long-term treatment of Pulmonary Arterial Hypertension | Approved: 04 June 2020 (D-20.178 / EDMS-RIM-264693) |

Source data for the analyses are provided as Statistical Analysis Software (SAS®) data sets according to Clinical Data Interchange Standards Consortium Study Data Tabulation Model (SDTM). Source data are those provided by Actelion Clinical Development Data Management (CDDM) via Statistical Programming And Computing Environment (SPACE) system. To prevent a violation of China's Human Genetic Resources (HGR) Regulation, data of participants in China for A303 that were due beyond 20 December 2019 are either not collected in clinical database or will be excluded from SDTM.

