1.2. Study Design

This is a multicenter, open-label study to assess long-term safety and tolerability of selexipag in participants with PAH.

Participants (males or females aged 18 years or older) from the study A302 were enrolled between 07 July 2010 and 02 September 2014 in this A303 study. This participant population consists of 3 cohorts:

- Cohort 1: Participants who completed the study A302 including the Treatment Extension Period (TEP) as scheduled per protocol (i.e., treated until unblinding of the study) without morbidity event.
- Cohort 2: Participants who experienced a morbidity event (had to be confirmed by the Critical Event Committee [CEC]) during the study A302.
- Cohort 3: Participants who experienced a worsening of PAH during the TEP of A302 and for whom a written approval to enter study A303 had been obtained from the sponsor.

The study is conducted in 155 centers in 39 countries.

Visit 1 in the A303 study should correspond to the last visit in study A302. If this was not possible, Visit 1 had to be performed not later than 2 weeks (14 days) after the last visit in study A302.

Participants of Cohort 2 and Cohort 3 were enrolled in the A303 study without knowledge of their previous treatment to preserve the integrity of the double-blind A302 study. All these participants entered the titration period of A303, i.e., they started selexipag at the lowest dose (200 µg bid).

Participants of Cohort 1 were eligible to enter the A303 study with knowledge of their previous study intervention allocation (selexipag or placebo). Participants who were receiving selexipag in A302 directly entered the maintenance period in A303 at the same dose of selexipag they were receiving at the end of the A302 TEP, except participants who were with treatment interruption ≥ 3 days between studies would enter the titration period of A303. Participants who were receiving placebo in A302 entered first the titration period of A303, i.e., started selexipag at the lowest dose (200 µg bid). Participants with a treatment interruption of at least 3 days between both studies (irrespective of whether randomized to selexipag or placebo) also entered the titration period of A303.

Treatment in the titration period of A303 was started at a selexipag dose of 200 µg bid with subsequent up-titration by 200 µg bid increments to achieve the individual MTD (maximum

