1600 µg bid) for administration during the maintenance period. Maintenance treatment was planned to continue until the earliest of (1) selexipag becoming commercially available in this indication in the participant's country, (2) the sponsor deciding to stop the A303 study, or (3) the participant or the investigator deciding to discontinue study intervention.

[figure not shown]
Each participant had his/her selexipag dose up-titrated up to his/her individual highest tolerated dose. Participants would receive new medication bottles at Visit 1, Visit 5 and every 6 months until the end of the A303 study. If a participant would enter the titration period, additional medication bottles would be given at Visit 2, 3, and 4.

At the end of the open-label study or after permanent discontinuation of study intervention, the end of study (EOS) visit will be performed and a post-treatment safety follow-up period will follow (30 days as recommended in the protocol; this is the last planned contact date).

The Data Monitoring Committee involved in the study A302 have reviewed safety data from A303 study up to 01 July 2016 (date of disbandment of the committee).

No interim analysis was planned in the protocol.

Figure 1: Study design

Titration period was applied to participants with a morbidity event or PAH worsening during TEP, participants on placebo in study AC 065A302 and participants with treatment interruption ≥ 3 days between studies (Figure 1 above). More information about Titration period can be found in Sections 5.5.1.1 and 5.5.2.3.

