4. POPULATIONS (ANALYSIS SETS) FOR ANALYSIS

In GRIPHON (A302) and GRIPHON OL (A303), two consecutive trials, a participant could go through one or more periods, which form a specific treatment sequence from A302 to A303 as summarized in [Table 2](#). For each treatment sequence a participant is counted only once.

Table 2: Summary of Consecutive GRIPHON (A302) and GRIPHON OL (A303) Studies (Periods) and Treatment Sequence

| Treatment sequence | Consecutive periods for ADaM datasets | |
|----------------------------|---|---|
| | Period 1 | Period 2 |
| | AC-065A302 (A302) | AC-065A303 (A303) |
| Selexipag / selexipag | Selexipag ←----- analysis phase 1 -----→ ←----- analysis -----→ | Selexipag ←----- analysis phase 2 -----→ ←----- analysis phase 3 -----→ |
| Selexipag / not applicable | Selexipag ←----- analysis phase 1 -----→ ←----- analysis phase 3 -----→ | Not entered in Period 2 |
| Placebo / selexipag* | Placebo ←----- analysis phase 1 -----→ | Selexipag ←----- analysis phase 2 -----→ ←----- analysis phase 3 -----→ |

*Participants who received Placebo in A302 and did not enter in A303 are not shown because they are not included in any analysis per this SAP.

To provide comprehensive long-term safety information, two analysis sets will be used and are defined as follows ([Table 3](#)):

Table 3: Description of Analysis Sets

| Analysis Sets | Description |
|-----------------------------------|---|
| Treated Set – OL | The treated set - OL (OLS) includes all participants who received at least one dose of study intervention in the A303. This is a subset of the Selexipag-Treated Set defined below. Under this Analysis set, the following three groups will be summarized: 
 - Ex-Selexipag: participants who received Selexipag in A302 - Ex-placebo: participants who received placebo in A302 - Total A303 This analysis set consists of data collected during “Analysis phase 2” in Table 2 (baseline (BL) is defined in Section 5.1.5.1) |
| Selexipag-treated Set (A302+A303) | The Selexipag-treated set (STS) includes all participants who received selexipag treatment at any time during A302 or A303. Under this Analysis set, the following two groups will be summarized: |

Table 3: Description of Analysis Sets

| Analysis Sets | Description |
|---------------|---|

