5.5.2.1. Treatment-Emergent Adverse Events

Definition: The verbatim terms used in the CRF by investigators to identify adverse events will be coded using the MedDRA, version 22.0. Any AE occurring at or after the initial administration of study intervention (on Day 1 in STS [A302+A303] or OLS – see Section 5.1.2) through EOT plus 3 days is considered as treatment emergent (TE). If the event occurs on the day of the initial administration of study intervention, and either event time or time of administration are missing, then the event will be assumed to be treatment emergent. If the event date is recorded as completely missing, then the event will be considered as treatment emergent unless it is known to be prior to the first administration of study intervention based on partial onset date or resolution date. All reported treatment-emergent adverse events (TE-AEs) will be included in the analysis.

Population: All participants included in the STS (A302+A303) and OLS

Study Intervention: Selexipag

Outcome measures: Binary variables, occurrence for each of the following categories of TE-AEs, TE-SAEs and SAEs (Yes/No):

- All TE-AEs
- TE-Serious AEs (TE-SAEs), including fatal (by the tick box 'Yes' for 'Serious' in CRF)
- All SAEs occurring at or after the initial administration of study intervention through EOT plus 30 days (instead of plus 3 days as for TE-SAEs)
- TE-AEs leading to discontinuation of study intervention (by the tick box 'Permanently discontinued' for 'Action taken with study drug' in CRF)
- TE-AEs by severity (by 'Maximum intensity' in CRF)
- TE-AEs by relationship to study intervention (defined as 'Related' or 'Unrelated' in CRF)
- TE-AEs leading to fatal outcome (by the tick box 'Death' for 'Outcome' in CRF)
- TE-AEs and TE-Serious AEs associated with COVID-19 infection.

- TE-AEs associated with COVID-19 infection leading to fatal outcome.

Summary method(s) for outcome measure:

- The (crude) incidence proportion defined as the percentage of participants who experienced at least 1 occurrence of a specific AE divided by the total number of participants.

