- All categories of TE-AEs will be summarized by SOC and PT, whereby the PT “Disease Progression” is only reported, if it is the only PT that the respective AE is coded to. The categories of All TE-AEs, TE-SAEs and SAEs will also be summarized by PT. An overall summary of all TE-AE categories will be provided. This will include the TE-AEs associated with COVID-19 infection. TE-AEs associated with COVID-19 infection will be reported for OLS only.
- The exposure-adjusted incidence rate (EAIR) will be summarized by SOC and PT. TE-EAIR is defined as the number of participants exposed to the intervention and experiencing a certain event divided by the total exposure duration of all participants who are at risk for the event. Specifically, for participants with no such event, the at-risk exposure duration is calculated from the Day 1 to EOT + 3 days; for participants with at least one event of a certain SOC or PT, the at-risk exposure duration is calculated from Day 1 to the first onset of such event.
- The TE-AE summaries above will also be reported for subgroups by PAH medication at baseline - Group 1 (defined in Section 5.6.8).
- TE-Serious AEs will also be summarized, by SOC and PT. In addition, serious TE-AEs will be summarized for subgroups by PAH medication at baseline - Group 1 (defined in Section 5.6.8).
- TE- AEs leading to discontinuation of study intervention will also be summarized, by SOC and PT. In addition, they will be summarized for subgroups by PAH medication at baseline - Group 1 (defined in Section 5.6.8).
- Severe TE-AE will also be summarized, by SOC and PT. In addition, severe TE-AEs will be summarized for subgroups by PAH medication at baseline - Group 1 (defined in Section 5.6.8).
- Related TE-AE will also be summarized, by SOC and PT. In addition, related TE-AEs will be summarized for subgroups by PAH medication at baseline - Group 1 (defined in Section 5.6.8).
- TE- AEs leading to fatal outcome will also be summarized, by SOC and PT. In addition, they will be summarized for subgroups by PAH medication at baseline - Group 1 (defined in Section 5.6.8).
- TE-Serious AEs associated with COVID-19 infection will also be summarized, by PT. The summary will report data from OLS only.
- TE-AEs associated with COVID-19 infection leading to death will be summarized too, by PT and for OLS only.

Listings of all AEs, SAEs and AEs with fatal outcome will be generated, separately, for STS (A302+A303) and OLS.

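### COVID-19 adverse event percentages are taken over all 709 open-label participants, including those who could not have a countable event, so they understate risk among those observed by a factor the SAP does not let the reader compute

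*SAP*

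**What the plan says.** SAP 5.5.2.1 lists "TE-AEs and TE-Serious AEs associated with COVID-19 infection" among its outcome measures, with fatal COVID-19 events as a further category. The one incidence proportion it defines for these outcomes is the "percentage of participants who experienced at least 1 occurrence of a specific AE divided by the total number of participants". It adds that "TE-AEs associated with COVID-19 infection will be reported for OLS only", and the separate serious and fatal COVID-19 summaries carry the same restriction.

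SAP Section 4 defines the OLS as the set that "includes all participants who received at least one dose of study intervention in the A303", with no calendar-time condition, and shows 330 ex-selexipag and 379 ex-placebo participants, 709 in total. According to SAP 1.2, participants "were enrolled between 07 July 2010 and 02 September 2014 in this A303 study". Treatment could end for several reasons, one of which was "selexipag becoming commercially available in this indication" in the participant's country.

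Under 5.5.2.1 an event counts as treatment-emergent only up to three days after the last dose. SAP Section 1 states that "data of participants in China for A303 that were due beyond 20 December 2019 are either not collected in clinical database" or will be left out of the source datasets; Appendix 2 (6.2) repeats this.

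Section 5.5.2.1 also plans an exposure-adjusted incidence rate (EAIR) by SOC and PT, with time at risk counted from Day 1. No section gives a separate denominator or start of risk for COVID-19.

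**The concern.** A percentage of participants with COVID-19 events will be read as the risk of COVID-19 illness while on selexipag. Only people on drug (or within three days of stopping) during the pandemic, and whose data were still being collected, could supply a case. Enrolment closed in September 2014, more than five years before the pandemic, and participants could leave through market availability, sponsor decision, personal or investigator decision, or death. Everyone who left earlier, and everyone under the China cut, adds to the denominator and nothing to the numerator.

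The study's sole objective is long-term safety, and the plan singles out serious and fatal COVID-19 events for their own tables. Percentages biased low by an unreported amount would go into the clinical study report, and nothing planned beside them shows how many participants were observable.

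**Working it through.** **Denominator.** SAP Section 4: 330 + 379 = 709, which matches the stated total. The two OLS columns use 330 and 379 and have the same problem.

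**Crude percentage.** Let c be the number of participants with a COVID-19 TE-AE and n the number of OLS participants with treatment-emergent time during the pandemic and outside the China cut. All c cases must come from these n people.

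- Reported: c/709
- Among those observable: c/n
- Understatement factor: (c/n) / (c/709) = 709/n

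The factor does not depend on c. It exceeds 1 as soon as one OLS participant stopped before the pandemic or falls under the China cut. The documents do not give n, so the values of n below are assumptions, as are the 20 cases used for illustration.

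| Share still at risk | n | 709/n | 20 cases over 709 | 20 cases over n |
|---|---|---|---|---|
| 80% | 567 | 1.25 | 2.8% | 3.5% |
| 60% | 425 | 1.67 | 2.8% | 4.7% |
| 40% | 284 | 2.5 | 2.8% | 7.0% |
| 20% | 142 | 5.0 | 2.8% | 14.1% |
| 10% | 71 | 10 | 2.8% | 28.2% |

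A factor of 2 needs n of 354 or fewer (709/2 = 354.5). A factor of 3 needs 236 or fewer (709/3 = 236.3).

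**What annual loss would produce these factors.** Assume uniform entry over the enrolment window, which puts entry 5.33 to 9.49 years before 1 January 2020 (assumed pandemic start), and a constant annual loss L from all causes, including the China cut. With h = -ln(1 - L), the share remaining is [exp(-5.33h) - exp(-9.49h)] / (4.16h). Its inverse, the factor, is 1.5 at 5% a year, 2.2 at 10%, 3.3 at 15%, 5.0 at 20% and 8.0 at 25%.

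**Exposure-adjusted rate.** The last enrolment was on 2 September 2014, so anyone still treated on 1 January 2020 carries at least 5.33 years of earlier time. From that date to 23 September 2021 (approval of SAP version 2.0, used here as an assumed end of treatment) is 1.73 years. The ratio of counted time to pandemic time is then at least (5.33 + 1.73)/1.73 = 4.1. If treatment ran to the end of 2021 it is (5.33 + 2.0)/2.0 = 3.7. Earlier enrolment or earlier stopping raises it, and participants who left before 2020 add counted time with no pandemic time.

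**Contrast within the SAP.** Other rows do remove people who cannot contribute. Maintenance-period reactions exclude participants who stopped during titration (5.5.1.2, 5.5.2.3), and treatment-emergent marked laboratory abnormalities exclude those already abnormal at baseline (5.5.3.1).

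**The case against.** A reader might infer that the percentages are understated several-fold, or that most of the 709 were never observed during the pandemic. The documents do not support either statement. They give no count on treatment in 2020-21, no count of participants in China and no count of exits through market availability. SAP 1.2 gives a stopping rule, and disposition (5.2) and exposure (5.5.1) are planned outputs only. A factor below 2 is not excluded. This objection stands in full, and the size has to be left as a range that starts near 1.

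The proportion is labelled crude and is arithmetically correct as a share of the OLS. Counts are shown with percentages, and adverse event listings are planned. That is true, but none of these outputs tells the reader how many people could have had an event.

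The EAIR is specified generically, and the bullets on COVID-19 tables do not mention it. That stands: dilution of the rate is conditional on its being applied to COVID-19 terms.

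SAP version 2.0 was checked against the data presentation specifications, which are not among the documents. A table-level denominator or footnote there cannot be ruled out. This limits certainty, but the SAP itself states the rule without one.

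Finally, this is a single-arm descriptive study with no hypothesis, and COVID-19 is neither a protocol endpoint (Protocol 3.8.2) nor a category of special interest (SAP Appendix 8). That stands and bears on severity.

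**Conclusion.** The point holds in direction, but the documents do not fix its size. As written, the COVID-19 TE-AE, TE-SAE and fatal TE-AE percentages divide by 709 and so understate risk among those under observation by 709/n, with n not given. Over the assumed shares of 80% down to 10% still at risk, the factor runs from 1.25 to 10. The use of 709 is inferred from the general rule combined with the OLS restriction; no sentence states it for COVID-19 separately.

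The EAIR would not cure this. If applied to COVID-19 terms it is diluted about 4-fold or more, assuming a pandemic start of 1 January 2020 and treatment running no later than September 2021; a later end lowers the minimum.

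Severity is moderate to minor. No comparison or primary result depends on these rows, but they are pre-specified safety figures that are open to misreading.

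**What to change.** In SAP 5.5.2.1, define a COVID-19 at-risk subset: OLS participants with at least one treatment-emergent day (to EOT + 3 days) on or after a stated pandemic start date, excluding participants subject to the China data cut. Report the COVID-19 TE-AE, TE-SAE and fatal rows over that subset, overall and by OLS column, and print its n. Start any COVID-19 EAIR time at risk on the same date.

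The sponsor should choose and justify the date. The 1 January 2020 used above is an assumption, and the only pandemic-specific date in the documents is the approval of the protocol's COVID-19 appendix on 16 June 2020. The percentage over 709 can stay alongside, so that these rows remain consistent with the overall TE-AE summary.

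The cost is one added SAP sentence and one population flag, built from end-of-treatment dates and the China cut. The resulting percentages will be less favourable.

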5.5.2.2. Adverse Events of Special Interest

Definition: See Section 6.8 for the list of adverse events in each adverse events of special interest (AESI) category. Any AESI occurring at or after the initial administration of study intervention (in STS or OLS – see Section 5.1.3) through EOT plus 3 days is considered as treatment emergent.

Population: All participants included in the STS (A302+A303) and OLS

Study Intervention: Selexipag

Outcome measures: Binary variables, occurrence of each category (Section 6.8) of treatment-emergent adverse events of special interest (TE-AESI), (Yes/No):

Summary method(s) for outcome measure:

- Number and percentage of participants with at least one TE-AESI.
- Number and percentage of participants with at least one TE-AESI leading to discontinuation of study intervention.
- Number and percentage of participants with at least one serious TE-AESI.
- Number and percentage of participants with at least one TE-AESI with a fatal outcome.
- Number of recurrent TE-AESIs (Participants may have multiple preferred terms [PTs] under a TE-AESI or/and multiple occurrences of a PT. The total number of occurrences of any PT in each TE-AESI category will be used).
- Total TE subject-years of treatment (Section 5.5.1)
- Average annualized event rate is calculated as the sum of numbers of recurrent TE-AESIs of individual participants in a treatment group/total TE subject-years of treatment
- Observed PTs (if a participant had multiple occurrences of a PT, this participant is counted only once)
- Severity (if a participant had multiple occurrences of a PT with different severity levels, this participant is counted only once in the worst severity level)

Separate listings of TE-AESIs will be generated for STS (A302+A303) and OLS.

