3.9.1.2.2 Laboratory parameters

Hematology and blood chemistry

Hematology and blood chemistry tests will be performed at Visit 1, if the last assessments in AC-065A302/GRIPHON were performed more than 4 weeks ago, and then at every visit until EOS. They include hemoglobin, hematocrit, platelet, leukocyte and erythrocyte counts, liver aminotransferases (AST/ALT), alkaline phosphatase, total and direct bilirubin, creatinine, urea, glucose, sodium, potassium, and albumin.

Local assessment of thyroid function (Thyroid-stimulating hormone, free triiodothyronine, free thyroxin) may be performed for individual patients if deemed clinically indicated by the investigator.

Pregnancy test (for women of childbearing potential)

Monthly urine (or serum) pregnancy tests must be performed from Visit 1 and up to at least 1 month after permanent discontinuation of the selexipag treatment. The monthly urine pregnancy tests are performed by the patient at home with validated kits provided by the site, or during a scheduled visit, or in a local laboratory. A serum pregnancy test is mandatory if pregnancy is suspected during the course of the study. Results of pregnancy tests will be documented in the patient's records (pregnancy test card).

Any pregnancy occurring during the treatment period and up to 30 days after study drug discontinuation must be reported immediately to the Actelion Drug Safety Department using the Actelion Pregnancy Form [Section 4].

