3.10.4 End of study visit or permanent discontinuation of study drug

Actelion will notify all sites when the end of study will occur. It can be at different dates depending on the sites and/or the country (see definition in Section 1.4.6). For all patients still participating to the study, the EOS visit must be scheduled within 4 weeks after the end of study notification.

For patients prematurely discontinuing selexipag treatment, it is recommended to perform the EOS visit within 7 days of the last study drug intake.

This visit includes:

- Physical examination
- Recording of AEs/SAEs
- Concomitant medication
- Measurement of vital signs and body weight
- Laboratory tests including:
 - Hematology
 - Blood chemistry
- Urine pregnancy test (for women of childbearing potential)
- Return of unused medication including empty bottles.

3.10.5 30-day follow-up

All patients will be contacted by phone 30 to 37 days after study drug discontinuation (safety follow-up call) [Sections 4.2.4 and 4.3.2].

- Urine pregnancy test result for women of childbearing potential

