5.5.1.2. Treatment-emergent Exposure Durations

For estimating the average annualized event rates of treatment-emergent adverse events of special interest (Section 5.5.2.2 and 5.5.2.3), the treatment-emergent (TE) exposure durations (in days) of individual participants are required and calculated as [EOT+ 3 days] – Day 1 + 1 day. The TE exposure duration in months is calculated as (duration in days / 30.4) and in years (also called TE subject-years) as (duration in days / 365.25). The total TE exposure duration of a treatment group is the sum over individual participants of that treatment group, and the average TE exposure duration is the total duration divided by the number of participants of that treatment group.

For prostacyclin associated reactions (Section 5.5.2.3), additional TE exposure durations of individual participants are defined for the titration and maintenance periods.

- The TE exposure duration of the titration period will be calculated as:
 - If the participant did NOT prematurely stop the study intervention before Day 86: TE exposure duration (days) = 86.
 - If the participant prematurely stopped the study intervention before Day 86: TE exposure duration (days) = [EOT+ 3 days] – [Day 1] + 1 (Section 5.1.3).
- The TE exposure duration of the maintenance period will be calculated as:

- If the participant did NOT prematurely stop the study intervention before Day 86: TE exposure duration (days) = {[EOT +3 days] – [Day 1] + 1} – 86 (Section 5.1.3).
- If the participant prematurely stopped the study intervention before Day 86: TE exposure duration will not be calculated, and the participant will be excluded from the denominator.

For a period (titration or maintenance) the TE subject-years of individual participants are calculated as (period-specific duration in days / 365.25). The total TE subject-years for a period of a treatment group is the sum over individual participants included in the respective period of that treatment group.

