6.8. Appendix 8 Adverse Events of Special Interest

The following adverse events of special interest will be used for selexipag. These are based on the important identified and potential risks in the latest Risk Management Plan and on-going discussion with Pharmacovigilance Risk Assessment Committee.

| AE Special Interest Category |
|--|
| Anaemia |
| Bleeding events |
| Gastrointestinal disturbances denoting intestinal intussusception (manifested as ileus or obstruction) |
| Hyperthyroidism |
| Hypotension |
| Light-dependent non-melanoma skin malignancies |
| Major adverse cardiovascular events (MACE) |
| Medication errors |
| Ophthalmological effects associated to retinal vascular system |
| Pregnancy |
| Pulmonary venoocclusive disease associated with pulmonary oedema |
| Renal function impairment / acute renal failure |
| Prostacyclin associated reactions* |

*Prostacyclin associated reactions will be summarized separately from other AESIs

Adverse events of special interest are defined in the aesi220.xlsx file available in SPACE.

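### The special-interest category Pregnancy is summarised only to EOT + 3 days and over all participants, men included; it needs a denominator of women and a count to EOT + 30 days

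*SAP*

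**What the plan says.** **SAP.** Section 6.8 opens with "The following adverse events of special interest will be used for selexipag", and its table includes Pregnancy. Section 5.5.2.2 sets one rule for all categories:

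- Window: an event from first dose "through EOT plus 3 days is considered as treatment emergent".
- Population: "Population: All participants included in the STS (A302+A303) and OLS".
- Percentage: "Number and percentage of participants with at least one TE-AESI".
- Annualised rate: "sum of numbers of recurrent TE-AESIs of individual participants in a treatment group/total TE subject-years of treatment". Under 5.5.1.2, "The total TE exposure duration of a treatment group is the sum over individual participants of that treatment group".

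The SAP text has no exception for pregnancy. Section 1.2 says that both sexes were enrolled. Section 5.5.2 defines adverse events as those on the AE pages of the two CRFs.

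**Protocol.** Section 3.9.1.2.2 asks for monthly tests until at least one month after permanent discontinuation and adds: "Any pregnancy occurring during the treatment period and up to 30 days after study drug discontinuation must be reported immediately". Section 4.4.2 gives the same window as the first month after discontinuation. It sends the report to drug safety on a Pregnancy form, and to an AE page where applicable. Section 3.10.5 says "All patients will be contacted by phone 30 to 37 days after study drug discontinuation (safety follow-up call" and lists a pregnancy test result at that contact.

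**The concern.** The protocol treats pregnancy differently from other adverse events: it has its own reporting form, its own tests and a reporting window that runs well past the general 3-day limit. The SAP applies the general limit to it, so the treatment-emergent special-interest table and listing leave out the last part of the period that the protocol watches.

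The denominator raises a second issue. Men, and women who are not of childbearing potential, cannot have the event but contribute to both the percentage and the subject-years. The printed figures will be lower than the figures among those at risk.

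SAP 6.8 bases the categories on the Risk Management Plan's risks, and SAP 1 says the completed summary can be used to update the submission tables. Few cases are to be expected, so one case in or out of the table, or a different denominator, changes what a reader sees.

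**Working it through.** **1. Denominators.** The group sizes are in SAP section 4. OLS: 330 + 379 = 709. STS: 574 + 379 = 953. Both reproduce the SAP's totals, and both include men.

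**2. Window gap.** The protocol's pregnancy window ends at EOT + 30 and the SAP's at EOT + 3: 30 − 3 = 27 days, that is, days 4 to 30 after the last dose.

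As a share of the watched time per participant this is 27 / (exposure days + 30), using the SAP's 30.4 days per month:

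- 12 months (illustrative): 27 / (364.8 + 30) = 6.8%
- 18.8 months (median selexipag exposure in A302, SAP 1): 27 / (571.5 + 30) = 4.5%
- 60 months (illustrative): 27 / (1824 + 30) = 1.5%

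These are shares of time. They are shares of cases only if the risk of pregnancy is constant.

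**3. Dilution.** Let f be the share of participants who can become pregnant. The planned percentage is c/N and the percentage among those at risk is c/(fN), so the planned figure is too low by a factor of 1/f. The same factor applies to the rate if those at risk have the same mean exposure as the whole group. The documents give neither the sex split nor the number of women of childbearing potential, so f is an assumption:

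| f (assumed) | 1/f | STS at risk | One pregnancy, STS | OLS at risk | One pregnancy, OLS |
|---|---|---|---|---|---|
| all (as planned) | 1 | 953 | 0.105% | 709 | 0.141% |
| 0.9 | 1.11 | 858 | 0.117% | 638 | 0.157% |
| 0.5 | 2.0 | 476.5 | 0.210% | 354.5 | 0.282% |
| 0.3 | 3.33 | 286 | 0.350% | 213 | 0.470% |

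**4. Other outputs that might fill the gap.**

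- The SAE summary to EOT + 30 (SAP 5.5.2.1) takes in only serious events, and a pregnancy need not be serious. Protocol 4.3.2.3 also sends follow-up SAEs to the drug safety database only.
- The listing of all AEs (SAP 5.5.2.1) is not limited to treatment-emergent events, but it gives no rate and contains only AE-page entries. Protocol 4.1 and 4.2.4 end AE-page collection 3 days after discontinuation.
- A late case may therefore exist only on a Pregnancy form, which the SAP does not read.

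**5. The SAP's own practice elsewhere.** It uses EOT + 30 for SAEs (5.5.2.1) and for deaths (5.5.2.4). It removes participants who cannot have the event from the denominator for maintenance-period prostacyclin reactions (5.5.2.3) and for marked laboratory abnormalities already present at baseline (5.5.3.1). Pregnancy gets neither adjustment.

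**The case against.** **The 3-day window follows the protocol.** This stands. The protocol's endpoints (3.8.2), its treatment-emergent definition (4.2.1) and its AE-page collection (4.2.4) all stop at 3 days. A reader might infer that the SAP contradicts the protocol. It does not. The mismatch is between the protocol's general AE rule and its pregnancy rule, and the SAP carries over the general one.

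**Nothing shows that pregnancies are lost.** This also stands. Drug safety receives every reported case. A reader might further infer that every pregnancy found at the 30 to 37 day call falls outside the window. That confuses the date of the test with the date of onset. SAP 5.5.2.2 classifies by when the event occurs, and a pregnancy conceived on treatment but detected at the call could be dated inside the window. Protocol 3.10.4 also schedules a test at the end-of-study visit. The SAP does not say which date counts as onset, and its imputation rules (5.1.6) do not settle it.

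**The dilution is unknown and can be undone.** Partly right. Counts are not diluted, and sex is tabulated (SAP 6.3), so a reader could recompute a percentage per woman. Women's subject-years are not among the planned outputs described, so the rate could not be recomputed. A reader might take the dilution to be 5-fold, but that needs f = 20%, which nothing in the documents supports.

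**Unseen files may settle it.** Possible. The category terms are in a separate file, and the data presentation specifications are not available here. Either might set another denominator.

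**Conclusion.** The point holds as a minor reporting improvement. For Pregnancy, the planned summary stops 27 days before the protocol's pregnancy window ends, and its percentage and rate are taken over a population that includes men. Pregnancies dated to days 4 to 30 are not counted in the treatment-emergent special-interest summary. The dilution is 1/f: about 1.1-fold to 3.3-fold for an assumed f of 90% to 30%, with the rate figure also assuming equal mean exposure.

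The documents do not show that any case is lost to the sponsor, or how many cases fall in the gap. The study is descriptive and no hypothesis test is affected. Extending the window alone would recover little, because the SAP reads only AE pages and the protocol does not require AE-page entries for events after day 3.

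**What to change.** For Pregnancy only, in SAP 5.5.2.2 and 6.8:

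1. Compute the percentage and the annualised rate over women, with their subject-years. Use women of childbearing potential if that status is recorded. An age limit of 50 is not a substitute: the protocol's footnote to the inclusion criteria requires age over 50 together with 24 months of amenorrhea, and it has other criteria that do not depend on age.
2. Add a count and a listing of pregnancies with onset through EOT + 30 days, including those detected at the 30 to 37 day call. Draw on Pregnancy forms as well as AE pages. The cut-off is day 30; day 37 is only the end of the call window.
3. State that onset is dated by estimated conception, not by the date of the test.
4. If a rate is given for the longer window, use person-time to EOT + 30, so that events and exposure cover the same period.

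The cost is a few sentences in the SAP, a reconciliation of pregnancy cases with the drug safety database, and a slightly less favourable printed figure. No new data collection from participants is needed.
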